4.3 Treatment Administration

Agent	Dose	Route	Schedule	Cycle Length
Cabozantinib	40 mg (starting dose)	PO	QD	4 Weeks (28 days)
Temozolomide	150 mg/m ² (starting dose for Cycle 1), then 200 mg/m ² (Cycles 2+)	PO	QD Days 1-5 of each cycle	

4.3.1 Temozolomide Administration

Subjects will take capsules of temozolomide by mouth QD, Days 1-5 during the first week of the cycle and none for the remainder of the cycle. Temozolomide should be taken on an empty stomach (1 hour before or 2 hours after meals or at bedtime) with full 8 ounces of water.

4.2.2 Cabozantinib Administration

Subjects will receive cabozantinib orally at a (starting) dose of 40 mg once daily. Cabozantinib should be swallowed whole with at least 8 ounces of water on an empty stomach at approximately the same time every day. Subjects must be instructed not to eat for at least 2 hours before and at least 1 hour after taking cabozantinib. If a subject misses a dose, the dose may be taken later only if it is within 12 hours of when the missed dose

should have been taken. The missed dose should not be made up if it is within 12 hours of the next scheduled dose. The tablets should not be crushed. Grapefruit, grapefruit juice, Seville oranges and their products should be avoided by subjects taking cabozantinib.

4.4 Toxicity Management & Dose Delays/Modifications/Discontinuation

Any subject who receives at least one dose of study therapy will be evaluable for toxicity endpoints. Each subject will be assessed for the development of toxicity according to the timeframe referenced in [Section 5.0](#) Study Procedures Table). Toxicity will be assessed according to CTCAE v.5.0.

The following should be taken into consideration in decisions regarding dose modifications (reductions or interruption) (please refer to [Appendix A](#) for dose modification algorithms for potential combination treatment related adverse events).

As a general approach all AEs should be managed with supportive care at the earliest signs of toxicity considered related to the study treatment. Should this be ineffective, dose interruptions and/or reductions should be considered to prevent worsening of toxicity.

The assigned starting dose for cabozantinib is 40mg/day. 20 mg dose reduction level of cabozantinib is permitted (see Table 0-1).

Dose modification criteria for cabozantinib are shown in Table 0-2. Dose interruptions and/or reductions should be implemented for unacceptable toxicity. Doses may be modified at any time while a subject is on treatment.

Dose reductions or interruptions may also occur in the setting of lower grade toxicity than defined in Table 0-2, if the investigator feels it is in the interest of a subject's safety and will optimize drug tolerability.

Interruption of cabozantinib treatment for cabozantinib-related AEs may occur at any time per investigator discretion. If treatment is interrupted due to related AEs for more than 6 weeks, cabozantinib should be discontinued unless there is unequivocal evidence that the subject is benefitting. In this situation, a subject may be able to restart therapy with a dose reduction upon resolution of the toxicity per the discretion of the investigator.

Dose interruptions for reason(s) other than related AEs (e.g., surgical procedures) can be longer than 6 weeks per the discretion of the investigator.

Drug interaction and increased toxicity is not anticipated; however, there is limited clinical experience with the combination of cabozantinib and temozolomide. To exclude prohibitive toxicity, up to 14 subjects will be treated with combined therapy as outlined above. If a subject goes off treatment before completing a 4 week observation period of safety run-in for reasons other than toxicity, then that subject should be replaced. Accrual will be interrupted after the initial 14 subjects have been enrolled. All subjects in the run-in cohort will be observed for at least 2 weeks after completion of Cycle 1 for toxicities.

Table 0-1: Dose Reductions of Cabozantinib

Assigned Dose	First Dose Level Reduction	Second Dose Level Reduction
40-mg cabozantinib oral qd	20-mg cabozantinib oral qd	No dose reduction permitted
qd, once daily Cabozantinib will be discontinued if a qd dose of 20-mg cabozantinib (minimum dose) is not tolerated		

Table 0-2: Dose Modifications of Cabozantinib for Treatment-Related Averse Events

CTCAE v.5.0 Grade	Recommended Guidelines for Management ^a
Grade 1 AEs	
 Add supportive care as indicated. Continue cabozantinib treatment at the current dose level if AE is manageable and tolerable.

Grade 2 AEs which are tolerable and are easily managed	
 Continue cabozantinib treatment at the current dose level with supportive care.
Grade 2 AEs which are intolerable and cannot be adequately managed	
 At the discretion of the investigator, cabozantinib may be dose reduced or interrupted. 
*Note: It is recommended that dose holds be as brief as possible.

Grade 3 AEs (except clinically non-relevant laboratory abnormalities)	
 Cabozantinib should be interrupted unless the toxicity can be easily managed with a dose reduction and optimal medical care. 
*Note: It is recommended that dose holds be as brief as possible.

Grade 4 AEs (except clinically non-relevant laboratory abnormalities)	
 Subjects should have cabozantinib interrupted immediately. Discontinue cabozantinib unless the following criteria are met: 
 Subject is deriving clear clinical benefit as determined by the investigator Toxicity can be managed with a dose reduction following recovery to Grade 1 (or baseline) and optimal medical care

^a Study treatment dose adjustment is only needed if the toxicity was deemed related to cabozantinib treatment or had an unclear relationship to cabozantinib treatment.
 
See Section 4.4.3 for additional instructions for management of cabozantinib related adverse events
	

4.4.1 Cabozantinib Dose Reinstitution and Reescalation

See [Section 4.4](#) for permitted timeframes for dosing delays and interruptions.

If the subject recovers from his or her toxicities to CTCAE v.5.0 Grade ≤ 1 or to the baseline value (or lower) and the toxicity was unrelated to study treatment, then study treatment may be restarted with no change in dose.

If the subject recovers from his or her toxicities to Grade ≤ 1 or to the baseline value (or lower) the toxicity was deemed possibly related to study

treatment, then study treatment may be restarted at a reduced dose (see Table 0-1 for the schedule of dose reductions).

Subjects receiving a daily dose of 20 mg may be restarted at the same dose if deemed safe at the discretion of the investigator. Subjects unable to tolerate a daily dose of 20 mg should discontinue study treatment.

Re-escalation to the previous dose, (but not higher than 40 mg/day) may be allowed at the discretion of the investigator for AEs which have resolved or recovered to Grade 1 (or baseline value) and deemed tolerable and easily managed by optimized supportive treatment. Dose re-escalation is not allowed for a drug-related dose reduction triggered by Grade 4 hematologic toxicities or by Grade 4 AEs affecting major organs (e.g., central nervous system, cardiac, hepatic, and renal).

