4.4.4 Management of Temozolomide Related Adverse Events

The most common adverse reactions ($\geq 10\%$ incidence) are: alopecia, fatigue, nausea, vomiting, headache, constipation, anorexia, convulsions, rash, hemiparesis, diarrhea, asthenia, fever, dizziness, coordination abnormal, viral infection, amnesia, and insomnia.

The most common Grade 3 to 4 hematologic laboratory abnormalities ($\geq 10\%$ incidence) that have developed during treatment with temozolomide are: lymphopenia, thrombocytopenia, neutropenia, and leukopenia.

Allergic reactions have also been reported.

Please refer to [Appendix A](#) for dose modification algorithms for potential combination treatment related adverse events.

Table 0-8: Temozolomide Dosing Interruption or Discontinuation during Treatment Period

Toxicity	Temozolomide Interruption	Temozolomide Discontinuation	Reduce Temozolomide by 1 Dose Level
Absolute Neutrophil Count (ANC)	≥ 0.5 and $< 1.5 \times 10^9/L$	$< 0.5 \times 10^9/L$	≥ 0.5 and $< 1.0 \times 10^9/L$
Platelet Count	≥ 10 and $< 100 \times 10^9/L$	$< 10 \times 10^9/L$	≥ 10 and $< 50 \times 10^9/L$
NCI-CTCAE non-hematological toxicity (except for alopecia, nausea and vomiting)	Grade 2	Grade 3 or 4	Grade 3

Treatment with temozolomide may be continued when all of the following conditions are met:

- $ANC \geq 1.5 \times 10^9/L$
- Platelet count $\geq 100 \times 10^9/L$
- NCI-CTCAE non-hematological toxicity \leq Grade 1 (except for alopecia, nausea and vomiting)

Table 0-9: Temozolomide Dose Levels

Dose 0 (Assigned Starting Dose)	Dose Level 1	Dose Level 0	Dose Level -1
150 mg/m ² /day	200 mg/m ² /day	150 mg/m ² /day	100 mg/m ² /day

Please see [Appendix B](#) for Daily Dose Calculations by Body Surface Area (BSA).

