Grade 2	
 • Cabozantinib treatment may be continued if PPES is tolerated. • Cabozantinib should be dose reduced or interrupted if PPES is intolerable. • Continue urea 20% cream twice daily AND high potency steroid cream (e.g., clobetasol 0.05%) once daily and add analgesics (e.g., NSAIDs/gamma-aminobutyric acid agonists) for pain control if needed. 
Reassess at least weekly; if PPES worsens or affects self-care, proceed to the intervention guidelines for Grade 3.
 
 • Continue temozolomide at the investigator's discretion
Grade 3	
 • Interrupt cabozantinib treatment until severity decreases to Grade 1 or 0. • Continue treatment of skin reaction with high potency steroid cream (e.g., clobetasol 0.05%) twice daily AND analgesics. • Resume study drug at a reduced dose if PPES recovers to Grade ≤ 1. • Discontinue subject from study treatment if PPES does not improve within 6 weeks • Interrupt/continue temozolomide at the investigator's discretion
Proteinuria (UPCR)	
≤ 1 mg/mg (≤ 113.1 mg/mmol)	
 • No change in cabozantinib or temozolomide treatment
> 1 and < 3.5 mg/mg (> 113.1 and < 395.9 mg/mmol)	
 • Refer to Table 0-6 for the management of cabozantinib treatment. No change in temozolomide treatment
≥ 3.5 mg/mg (≥ 395.9 mg/mmol)	
 • Refer to Table 0-6 for the management of cabozantinib treatment. No change in temozolomide treatment.
Nephrotic syndrome	
 • Discontinue cabozantinib
Hepatocellular Toxicity	
Grade 2 AST or ALT or Total Bili lasting longer than a week	
 • Interrupt cabozantinib and temozolomide until Grade 1. • Refer to the Section 4.4.3.13 for the management of DILI
Other Treatment Related Adverse Events (such as fatigue, nausea, vomiting, anorexia, weight loss, etc)	

Grade 1 or Grade 2 (tolerable)	
 • Add supportive care as indicated. • Continue cabozantinib and temozolomide treatment at the current dose; monitor as clinically indicated

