Intolerable Grade 2 or Grade 3	
 • Interrupt cabozantinib and temozolomide treatment until it is a Grade 1 or tolerable grade 2. Restart both cabozantinib and temozolomide at the current dose or dose reduced by one level.^b For Grade 3 AEs related to Temozolomide dose reduce by one level. • *Note: It is recommended that dose holds be as brief as possible
Grade 4-related to temozolomide Grade 4-related to cabozantinib (except clinically non-relevant laboratory abnormalities)	
 • Discontinue temozolomide. • Subjects should have cabozantinib interrupted immediately. • Discontinue cabozantinib unless the following criteria are met: Subject is deriving clear clinical benefit as determined by the investigator Toxicity can be managed with a dose reduction following recovery to Grade 1 (or baseline) and optimal medical care
Study treatment dose adjustment is only needed if the toxicity was deemed related to cabozantinib treatment or had an unclear relationship to cabozantinib treatment. ^b except nausea, vomiting, and alopecia- no dose interruption required for temozolomide	

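### For related fatigue, anorexia, weight loss and similar AEs at tolerable Grade 2, Section 4.4.4 holds temozolomide while Appendix A gives it, and no text says which governs

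*Combined protocol and SAP*

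**What the plan says.** **Temozolomide, Section 4.4.4.** Table 0-8 lists non-hematological Grade 2 toxicity under interruption, with alopecia, nausea and vomiting excepted. Below the table the section adds: "Treatment with temozolomide may be continued when all of the following conditions are met". One of those conditions is non-hematological toxicity of Grade 1 or lower, with the same three exceptions.

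**Both drugs, Appendix A, row for other treatment-related AEs.** The row names fatigue, nausea, vomiting, anorexia and weight loss as examples.
- Grade 1 or tolerable Grade 2: "Continue cabozantinib and temozolomide treatment at the current dose; monitor as clinically indicated".
- Grade 3, or a Grade 2 that the subject cannot tolerate: the rule for the hold is "Interrupt cabozantinib and temozolomide treatment until it is a Grade 1 or tolerable grade 2", and the rule for resuming is "Restart both cabozantinib and temozolomide at the current dose or dose reduced by one level". For a Grade 3 AE related to temozolomide, that drug is reduced by one level.
- Footnote b: "except nausea, vomiting, and alopecia- no dose interruption required for temozolomide".

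**Cabozantinib, Section 4.4.1.** The sentence on possibly related toxicity begins "If the subject recovers from his or her toxicities to Grade", sets the level at 1 or lower or baseline, and continues "then study treatment may be restarted at a reduced dose".

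**Links between the texts.** Sections 4.4 and 4.4.4 refer the reader to Appendix A for combination-related AEs. Neither says that Appendix A overrides the body text, or the reverse.

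**The concern.** A site handling a subject with related fatigue at tolerable Grade 2 on the day a temozolomide course is due gets opposite instructions from two parts of the same protocol. Section 4.4.4 holds the drug and Appendix A gives it. Table 0-8 does not separate tolerable from intolerable Grade 2, so the two cannot be reconciled by treating them as different situations.

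What is at stake is subject safety and consistent dosing across sites. The study is multicenter, Section 4.4 acknowledges limited clinical experience with the combination, and Section 1.3 says the Cycle 1 temozolomide dose was modified because of observed toxicity. In that setting sites should not be choosing between two rules for continuing an alkylating agent during unresolved Grade 2 toxicity.

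**Working it through.** No sample size, power or error rate enters, so the check is a comparison of texts.

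**Inputs**
- Section 4.4.4: Table 0-8 (Grade 2 interrupts) and the condition list (continue at Grade 1 or lower), exempting alopecia, nausea and vomiting.
- Appendix A, other treatment-related AEs: the tolerable Grade 2 line, the intolerable Grade 2 or Grade 3 line, and footnote b.
- Section 4.3: temozolomide is taken on Days 1-5 of a 28-day cycle.

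**Step 1: which AEs are affected.** The row names five AEs. Nausea and vomiting fall under the Section 4.4.4 exception, and footnote b agrees. That leaves 5 - 2 = 3: fatigue, anorexia and weight loss. The row's list is open-ended, so other non-hematological AEs without a row of their own are affected in the same way.

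**Step 2: apply both rules to the same subject.** Temozolomide only, with a course due:

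| Situation | Section 4.4.4 | Appendix A | Agree? |
|---|---|---|---|
| Related fatigue at tolerable Grade 2, no prior hold | Interrupt; condition not met | Continue at current dose | No |
| Held for intolerable Grade 2 fatigue, now tolerable Grade 2 | Condition not met | Restart at current dose or one level lower | No |
| Held for Grade 3 fatigue related to temozolomide, now tolerable Grade 2 | Condition not met | Restart one level lower | No |
| Held for Grade 3 fatigue, now Grade 1 | Grade condition met | Restart | Yes, on recovery grade |
| Grade 2 nausea or vomiting | Exempt | No interruption required | Yes |

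Table 0-8 lists non-hematological Grade 3 under both discontinuation and one-level reduction. The Grade 3 lines above therefore assume that temozolomide was not discontinued.

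**Step 3: when a dose changes.** Temozolomide is given on 5 of 28 days. A subject who is at tolerable Grade 2 only between courses, and is back to Grade 1 before the next Day 1, is dosed the same way under either text. The conflict takes effect only if tolerable Grade 2 is present when a course is due or under way.

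**Step 4: precedence.** Section 4.4.4 points to Appendix A and then, in the same section, sets its own Grade 1 condition. A pointer followed by a stricter local rule is not a clear override in either direction.

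**Step 5: cabozantinib.** Section 4.4.1 describes restart at Grade 1 or lower, or baseline, and does not address tolerable Grade 2. Appendix A accepts that grade for restart. Table 0-2 continues cabozantinib at the current dose for tolerable, easily managed Grade 2 AEs. Section 4.8 counts recovery to tolerable Grade 2 or lower within 6 weeks as enough to avoid discontinuation. Three texts therefore accept the grade and one is silent.

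**The case against.** The best counter-argument is that Appendix A is the operative algorithm. It is written for the combination, both Section 4.4 and Section 4.4.4 send the reader to it, and a specific algorithm that the body text points to is normally followed. Section 4.8 also treats tolerable Grade 2 as adequate recovery. This is a reasonable reading, but it does not settle the matter for temozolomide. Section 4.4.4 requires all of its conditions to be met, gives a closed list of three exceptions and repeats the interruption in Table 0-8. Section 4.8 is a discontinuation rule and does not say when a held drug may resume.

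A reader might go further and infer that Section 4.4.1 forbids restarting cabozantinib at tolerable Grade 2, so that the protocol contradicts itself on both drugs. The text does not support that. The sentence is permissive and contains no restriction to that grade alone, and the later sentence on subjects already at 20 mg states no grade. Any cabozantinib dose difference calculated from that reading would rest on silence.

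A reader might also infer an effect on overall dose intensity or on the week-12 progression-free rate. Section 4.4.3 lists fatigue, decreased appetite and weight loss among AEs seen in at least 20% of cabozantinib-treated subjects, and Section 4.4.4 lists fatigue and anorexia among those seen in at least 10% on temozolomide. Neither list gives grades, and neither says how often such AEs settle at tolerable Grade 2. No frequency can be derived.

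**Conclusion.** The contradiction holds for temozolomide. For related non-hematological AEs in the Appendix A row for other AEs, outside alopecia, nausea and vomiting, Section 4.4.4 holds the drug at Grade 2 and Appendix A gives it at tolerable Grade 2, both without a prior hold and on restart after one. The size is one grade of toxicity at the time of a Days 1-5 course, for three of the five AEs named in the row and any unnamed AE handled by it.

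For cabozantinib the finding is only an ambiguity, and a minor one: Section 4.4.1 does not mention a recovery grade that Appendix A, Table 0-2 and Section 4.8 accept.

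The conclusion assumes a subject whose baseline is Grade 1 or lower and for whom temozolomide has not been discontinued under Table 0-8. The two-stage design's error rates and sample size are not affected. The change should be made because it removes opposing dosing instructions at little cost.

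**What to change.** 1. In both lines of the Appendix A row for other treatment-related AEs (tolerable Grade 2; intolerable Grade 2 or Grade 3), state that temozolomide is held at Grade 2, except for alopecia, nausea and vomiting. State also that, if it is not discontinued under Table 0-8, it resumes only when the Section 4.4.4 conditions are met.
2. If the sponsor intends temozolomide to be given at tolerable Grade 2, leave Appendix A as it is and amend Table 0-8 and the Grade 1 condition in Section 4.4.4 instead.
3. Add one sentence to Section 4.4.1: where Appendix A has a row for the AE, that row's restart threshold and dose govern cabozantinib. This leaves the investigator's present choice of restart dose intact.

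The cost is amendment wording in one Appendix A row and one sentence in Section 4.4.1, with no new procedures. The downside of option 1 is that some temozolomide courses will start later than Appendix A now allows. If the rule against making up missed doses (footnote j to the Section 5.0 table) is applied to held doses, some could be lost rather than delayed.

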4.4.2 Guidelines for Management of Potential Adverse Events

Subjects will be monitored for AEs from the time of signing informed consent through their last follow-up visit (30 days after the date of the last dose of cabozantinib treatment). Subjects will be instructed to notify their physician immediately at the onset of any AE. Seriousness, severity grade, and relationship to study treatment of AEs will be determined by the investigator. AE severity will be graded by the investigator in accordance with CTCAE v.5.0.

Management of severe or intolerable adverse reactions may require temporary dose reduction and/or interruption for cabozantinib.

4.4.3 Management of Cabozantinib Related Adverse Events

The most frequent AEs experienced by $\geq 20\%$ of subjects treated with cabozantinib in descending order of frequency were diarrhea, fatigue, decreased appetite, nausea, PPES, weight decreased, vomiting, hypertension, constipation, asthenia, dysphonia, and AST increased. For a full description of the safety profile of cabozantinib, refer to the current Cabozantinib Investigator's Brochure.

Other medically important but less frequent AEs including arterial thrombotic AEs (e.g., transient ischemic attack [TIA], and myocardial

infarction [MI]) and venous thrombotic AEs (e.g., deep vein thrombosis [DVT] and pulmonary embolism), severe hemorrhagic events, proteinuria, wound healing complications, gastrointestinal (GI) perforation, abscesses including intra-abdominal and pelvic abscess, GI and non-GI fistula formation, osteonecrosis, and reversible posterior leukoencephalopathy syndrome (RPLS).

Adverse events associated with laboratory abnormalities experienced by \geq 5% of subjects treated with cabozantinib in descending order of frequency were AST increased, ALT increased, anemia, hypothyroidism, hypokalemia, hypomagnesemia, thrombocytopenia, hypocalcemia, proteinuria, hypophosphatemia, ALP increased, lactate dehydrogenase (LDH) increased, neutropenia, lipase increased, hyponatremia, platelet count decreased, GGT increased, hypoalbuminemia, leukopenia, and blood TSH increased.

Adverse events may occur within the first few weeks in the course of treatment with cabozantinib, as cabozantinib is expected to reach steady state exposure at approximately 2 weeks following first dose. Events that generally have an early onset include hypocalcemia, hypokalemia, thrombocytopenia, hypertension, PPES, abdominal pain, mucosal inflammation, constipation, diarrhea, and vomiting. Adverse events should be managed with supportive care at the earliest signs of toxicity. Dose reductions and treatment interruptions should be considered. Dose reductions are recommended for events that, if persistent, could become serious or intolerable.

Cabozantinib should be discontinued for the following AEs: visceral perforation or fistula formation, severe hemorrhage, serious arterial thromboembolic events, nephrotic syndrome, hypertensive emergency, persistent uncontrolled hypertension despite optimal medical management, and RPLS.

